5.1 Efficacy Evaluation (if applicable)

N/A

5.2 Pharmacokinetic Evaluation (if applicable)

N/A

5.3 Safety Evaluations

- 1) 7T MRI safety screening form
- 2) Pregnancy tests prior to each fMRI for women of childbearing potential
- 3) Columbia-Suicide Severity Rating Scale (C-SSRS), administered if the subject expresses any suicidality or thoughts that are concerning to the therapist.
- 4) If a participant reports any significant distress or refusal during the diagnostic interview session, he or she will be withdrawn immediately. If a participant reports any significant distress or refusal during the brain imaging session, he or she will be withdrawn immediately.
- 5) If a participant reveals information that they did not reveal during the screen that prevents them from participating (e.g., metallic device), or if tests positive for urine pregnancy screen, if female, they will be withdrawn from the study.

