Test Article(s) (If Applicable)	
Behavioral Activation Treatment for Anhedonia (BATA): We have modified Behavioral Activation Treatment for Depression to create Behavioral Activation Treatment for Anhedonia (BATA) which we will evaluate in this study by comparing its effects on brain functioning relative to treatment with Mindfulness-Based Cognitive Therapy (MBCT).

Study Design	Following a phone/online screen and an initial assessment session to confirm eligibility, participants will complete a baseline fMRI session at the UNC Biomedical Research Imaging Center (BRIC). They then will be randomized to receive a 15-week course of BATA (50%) or a 15-week course of Mindfulness Based Cognitive Therapy (MBCT) (50%) administered at Duke University Medical Center (DUMC). Both groups will receive pre- and post-treatment scans as well as two mid-treatment scans (weeks 8 and 12) to evaluate treatment BATA dose.
---------------------	--

Subject Population	Inclusion Criteria
key criteria for Inclusion and Exclusion:	
 1. 18-50 years old and treatment seeking; 2. SHAPS scores ≥ 20, corresponding to clinically significant anhedonia; 3. Clinician's Global Impression Scale-Severity score (CGI-S) ≥ 3 to assure a clinically impaired sample; 4. Seeking treatment for anhedonia (i.e., referred from an outpatient clinic or responded to an advertisement for anhedonia treatment; endorses desire for treatment during screening).

Exclusion Criteria

5. Those for whom medication management is the primary gold-standard treatment, including those with bipolar disorder/mania, schizophrenia spectrum, and other psychotic disorders;
6. Prior treatment with behavioral activation therapy for depression or mindfulness-based treatments (those with exposure to other forms of psychotherapy, e.g., supportive therapy, will be eligible);
7. Those who may have difficulty understanding the cognitive components of BATA, including those with intellectual disability, neurocognitive disorders, and dissociative disorders;
8. Feeding and eating disorders which may have confounding effects on the BOLD fMRI signal;
9. Substance Use Disorders given confounding effects of substances of abuse on the BOLD fMRI signal;
10. Suicidal intent and plan;

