Pregnancy: Although MRI poses no known risks to fetuses, pregnant woman will be excluded from participation according to UNC IRB policy that requires that all female research subjects of childbearing potential be given a urine pregnancy test immediately prior to the MRI scan session to rule out pregnancy.

Protections Against Risk

Symptom / Behavioral Measurements: To minimize the risk of a participant becoming stressed, the laboratory space will be designed to be patient-friendly. Breaks will be provided as requested, and assessors will be flexible in the pace and scheduling of assessments.

Treatment/Suicidality. Care will be taken to assure that no participant will be in danger of harming themselves. Any participant who reports suicidal intent will be immediately assessed using the Suicide Risk Assessment protocol. Based on the level of assessed risk, patients may be escorted to the Emergency Room for further evaluation. Participants who report a significant increase in psychiatric symptoms including suicidality will be

excused from the research protocol and referred for more extensive treatment, including referral for medications, if desired. Following the conclusion of the trial, all participants will be provided with referral information as appropriate for further treatment.

MRI: This MRI studies follow guidelines with regard to specific absorption ratio (SAR) and limits on gradient slew rate (dB/dt). Participants will be interviewed and will fill out a screening questionnaire for 7T imaging safety prior to entering the MRI suite. Participants will be instructed to remove all metal objects, including clothing with metal clasps, before entering the magnet room. Some participants may feel uncomfortable or confined once positioned within the MRI system. This potential reaction will be reduced by discussing the procedure prior to entry, by providing the participant with a mirror through which they can look out into the room, and by communicating with the participant over the intercom.

Confidentiality: To protect confidentiality, only alphanumeric ID numbers, rather than names, will appear on clinically sensitive charts and digital data. The key linking the alphanumeric identifier and participant's identity will be maintained on a separate drive that will be double password protected and to which only the PIs and key study personnel will have access. All research personnel will have completed HIPPA training for researchers and CITI training.

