
Psychotherapy sessions:

Both BATA and MBCT groups: up to 15 weekly 45-minute individual psychotherapy sessions

Scan sessions:

Both BATA and MBCT groups: scans will occur at week 8, week 12, and week 15 (final week): these will include administering the 7T MRI safety screening form, a urine pregnancy testing for women, and structural and functional MRI scans will be collected.

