4.7 Subject Completion/ Withdrawal procedures

Completion: Participants will complete the study after 15 weekly treatment sessions.

Withdrawal procedures. Patients may opt to discontinue participation at any time. Any patient who misses three consecutive scheduled appointments will be a dropout, and this will be explained to patients during consent and whenever a patient begins missing sessions. This operational definition of dropout will be used in data analyses.

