6.4 Statistical Methods

Aim 1, fMRI outcomes: Only patients who complete at least two therapy sessions will participate in post-treatment assessments. We will compare fMRI activation in regions of interest at pre- and post-treatment. The design is a 2 (BATA vs MBCT) X 2 (CN, rACC) X 2 (pretreatment vs post-treatment) ANCOVA testing the change from pre- to post-treatment as moderated by treatment group and brain region in the outcome variables. The Treatment × Time interaction beta will be used to evaluate whether BATA produces changes in neural responses to reward anticipation and reward outcomes that exceed our *a priori* target engagement criteria (increased right caudate nucleus (CN) activation during reward anticipation and decreased rostral anterior

cingulate cortex (rACC) activation during reward outcomes) and exceed changes due to MBCT. *Post-hoc* comparisons will compare change across each region.

Aim 2, anhedonia outcomes: To evaluate the effects of BATA, relative to MBCT, for on anhedonia symptoms treating anhedonia, we will test for differential change over time between those who receive BATA and those who receive MBCT post-treatment. We will use an intent-to-treat (ITT) analysis for patients who receive BATA relative to those who don't. The ITT model will be a repeated-measures ANCOVA with effects for treatment condition (BATA, MBCT), outcome measure (SHAPS), time (pre-treatment, post-treatment) and their interactions. The interaction tests will assess mean differences at each time point as well as differences in the degree of change between the groups. This also provides tests of each group relative to their baseline scores. We will include gender and age as covariates in these models.

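### Rules that withdraw randomised patients do not provide for continued SHAPS collection, and the Aim 2 model labelled intent-to-treat uses only pre- and post-treatment scores

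*Combined protocol and SAP*

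**What the plan says.** **Withdrawal at a scan.** Section 5.3, item 5, covers a participant who discloses something not disclosed at screening that rules out participation, with a metallic device as the example; it continues "or if tests positive for urine pregnancy screen, if female, they will be withdrawn from the study". The item names no week. Item 2 of the same list requires "Pregnancy tests prior to each fMRI for women of childbearing potential". Section 4.2 says of both arms that "scans will occur at week 8, week 12, and week 15 (final week): these will include administering the 7T MRI safety screening form", together with a pregnancy test. The synopsis (Study Design) places randomisation after the baseline scan.

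**Reason for the pregnancy rule.** Section 1.3 states that "pregnant woman will be excluded from participation according to UNC IRB policy", a policy tied to testing before MRI.

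**Other exits.** Section 1.3 (Suicidality) removes patients who endorse C-SSRS items 4 or 5. Section 1.3 (Protections Against Risk) removes those reporting a significant increase in psychiatric symptoms. Section 4.5 makes any psychotropic medication started during therapy exclusionary.

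**Withdrawal procedure.** Section 4.7 lets patients stop at any time and adds "Any patient who misses three consecutive scheduled appointments will be a dropout". It says nothing about later data collection.

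**SHAPS and its analysis.** Section 5 describes SHAPS as a 14-item self-report scale given by computer. The text list in section 4.2 schedules it at pre-treatment, week 8, week 12 and post-treatment. Section 6.4 labels the Aim 2 analysis intent-to-treat and specifies a repeated-measures ANCOVA with "outcome measure (SHAPS), time (pre-treatment, post-treatment) and their interactions". It names no method for a missing post-treatment score.

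**The concern.** A patient who can no longer be scanned can still fill in a questionnaire. As worded, item 5 ends participation in the whole study rather than in scanning, so an obtainable secondary outcome is given up for a reason that concerns only the scanner. The exits for suicidality, worsening and medication act in the same way and matter more, because the reason for leaving is related to the outcome.

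At stake is whether the Aim 2 comparison keeps everyone who was randomised. An analysis labelled intent-to-treat that needs a post-treatment score, with no follow-up after withdrawal, becomes in practice an analysis of those who stayed. If outcome-related exits differ between BATA and MBCT, the SHAPS comparison could be biased.

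**Working it through.** **1. Can the rule reach randomised patients?** Item 5 has no time limit. Item 2 and section 4.2 repeat the pregnancy test, and section 4.2 the 7T form, at weeks 8, 12 and 15. Randomisation follows the baseline scan. So yes, although most undisclosed metal should surface at the baseline scan, before randomisation.

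**2. Does anything keep SHAPS going?** Section 4.7 defines dropout. Section 4.3 offers referral information. Section 6.3 covers adverse events up to the final visit. Section 6.4, under Aim 1, says "Only patients who complete at least two therapy sessions will participate in post-treatment assessments", which restricts who is assessed and does not mention withdrawn patients. None provides for SHAPS after withdrawal.

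**3. Cost for pregnancy or metal.** The plan gives no withdrawal rate and no figure to reproduce. Inputs: 60 randomised, 30 per arm (synopsis). Assumption: one patient lost. Standard error of a standardised difference = √(1/n₁ + 1/n₂).

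- 30 and 30: √(1/30 + 1/30) = 0.2582
- 30 and 29: √(1/30 + 1/29) = 0.2604; ratio 0.2604/0.2582 = 1.009, or +0.9%

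The effect detectable with 80% power (two-sided 0.05, noncentral t) moves from 0.736 to 0.742 SD.

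**4. Range for withdrawals of all kinds (counts assumed).**

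| Lost per arm | SE | Change | Detectable effect (SD) |
|---|---|---|---|
| 1 | 0.2626 | +1.7% | 0.749 |
| 2 | 0.2673 | +3.5% | 0.762 |
| 3 | 0.2722 | +5.4% | 0.777 |

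Three per arm is not plausible for pregnancy alone. Three in 12 weeks among 30 women would imply a yearly rate of 1 − (1 − 3/30)^(52/12) = 37%; among 20 women, 1 − (1 − 3/20)^(52/12) = 51%.

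**5. Would continued collection raise power?** Not necessarily. Assume a true effect of 0.75 SD, two-sided 0.05, and 3 per arm who stop therapy.

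- Completers only, 27 and 27: power 77.2%
- All 30 and 30, half the effect in those who stopped: average effect 0.75 × (27 + 0.5 × 3)/30 = 0.7125; power 77.4%
- All 30 and 30, no effect in those who stopped: 0.75 × 27/30 = 0.675; power 72.9%

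**6. Would a better model suffice without follow-up?** With 3 per arm lacking a post-treatment score, a baseline-adjusted model that also uses their week 8 and week 12 scores leaves the standard error 2.4% to 4.5% above complete data. This is generalised least squares with weeks 0, 8, 12 and 15; correlations are assumed, either equal at 0.5 or 0.7, or decaying by those factors per 4 weeks. Completers alone give +5.4%, so the model recovers only part of the loss.

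**7. Size of a possible bias from outcome-related exits.** If k of 30 in one arm are missing and their mean differs by δ SD from that of the patients observed, the observed arm mean is off by kδ/30. For k = 1 to 3 and δ = 0.5 to 1.0 (assumed), that is 0.5/30 = 0.02 to 3/30 = 0.10 SD. Similar losses in both arms would largely cancel.

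**The case against.** **Silence is not prohibition.** Section 6.4 sets the bar for post-treatment assessment at two therapy sessions, not completion, so some non-completers may be assessed, and a patient at week 8 would normally qualify. With the intent-to-treat label, the study team might collect SHAPS anyway. This has weight: the documents do not forbid follow-up, so the loss of outcomes is an inference. But the sentence is a restriction under the fMRI aim, and it does not override withdrawal from the study.

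**The stated trigger is rare and the endpoint is secondary.** This stands. The primary endpoint is fMRI, and a patient who cannot be scanned cannot supply it. Stopping scans is right on safety and policy grounds.

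**A reader might infer that continued SHAPS restores full precision and therefore power.** That holds only for the standard error, and only if every withdrawn patient responds. If therapy stops, the effect may be diluted enough to cancel or outweigh the gain.

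**A reader might infer from the visit table that a patient withdrawn at the first mid-treatment scan has only a baseline score.** The table puts that scan at Day 42, while the text puts it at week 8 and also schedules SHAPS then. The table may have been damaged in extraction, so I rest nothing on its visit order.

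**Conclusion.** The gap is real and small. Followed as written, the plan can withdraw randomised patients, does not provide for SHAPS afterwards, and analyses Aim 2 with a model that needs a post-treatment score and ignores weeks 8 and 12. For pregnancy or metal the expected cost is about one patient, a standard error about 0.9% larger, with no bias shown; that count is my assumption.

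The stronger reason to act lies in exits for suicidality, worsening and medication, which are related to outcome. The documents give no rates for these, overall or by arm, so the bias range above is illustrative. A reader might conclude that the rules bias Aim 2 or threaten the trial; the documents do not support that, since nothing shows that exits will be frequent or differ by arm. The gain is adherence to intent-to-treat and protection against bias, not a promised increase in power.

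**What to change.** 1. **Section 5.3, item 5:** keep every scan safety rule, but for randomised patients have it stop further scanning only. Leave continuation of therapy to clinical judgement and IRB policy.
2. **Sections 1.3, 4.5, 4.7 and 5.3:** after any discontinuation, keep requesting the scheduled SHAPS (week 8, week 12, post-treatment) from patients who still consent, unless contact is clinically inappropriate.
3. **Section 6.4, Aim 2:** analyse all randomised patients by assigned arm in a likelihood-based mixed model with baseline, week 8, week 12 and post-treatment SHAPS (time categorical, arm by time, gender and age as covariates). Test the arm contrast at post-treatment.
4. **Reporting:** give withdrawals by arm and reason.

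Follow-up is the main remedy and the model is the back-up. The cost is protocol, consent and analysis-plan wording, IRB review because the pregnancy exclusion follows IRB policy, and a 14-item questionnaire for a few patients. The downside is that some scores will come after therapy has stopped or medication has started. The estimate then describes assignment to treatment, not completed treatment, and may be diluted.

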6 STATISTICAL CONSIDERATION

6.1 Primary Endpoint (fMRI)

Increase in right CN activation during reward anticipation and decrease in rACC activation during reward outcomes.

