11. Psychotropic medication use in the past 4 weeks (8 weeks for fluoxetine) and/or current psychotherapy. Participants must be medication-free at study entry; study personnel will not supervise medication taper for the purpose of the study, but those who taper under the supervision of their regular provider will be eligible;
12. Currently pregnant, as measured by urine pregnancy screen immediately before MRI scans;
13. Positive urinalysis screen for cocaine, marijuana, opiates, methadone, amphetamines, and benzodiazepines (conducted on-site via Biosite Triage Meter Plus) at study entry.
14. No neurological conditions (e.g., history of stroke, seizure, or TBI);
15. Contraindications for 7T imaging (criteria are more stringent than for 3T imaging): Metal in the body, dental work that is not fillings or gold, any tattoos, any metal in the body, any metal injury – especially those to the eyes, any other type of implant unless they are 100% plastic.

Number Of Subjects	60 subjects will be randomized such that half will receive BATA and half will receive MBCT.
---------------------------	---

Study Duration	Approximately 16 weeks
Study Phases	(1) Phone/online Screening : initial screening for eligibility.
Screening	(2) In-Person Screening : further screening for eligibility and consent
Study Treatment	(3) Baseline fMRI
Follow-Up	(4) Initiate up to approximately 15 weeks of therapy (experimental treatment (BATA) or comparison treatment (MBCT)) (5) Mid-treatment fMRI scans at approximately weeks 8 and 12. (6) Post-treatment fMRI scan.
Efficacy Evaluations	(1) fMRI activation in right CN during reward anticipation and rACC during reward outcomes (2) Anhedonia severity (SHAPS scores)
Pharmacokinetic Evaluations	N/A
Safety Evaluations	1) 7T MRI safety screening form completed before each scan session 2) Columbia-Suicide Severity Rating Scale (C-SSRS) completed if a subject endorses suicidal thoughts at therapy visits.

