6.5 Sample Size and Power

Power Analyses: In this study we will enroll 60 participants, whom will receive BATA treatment MBCT treatment. Based on our pilot data demonstrating increased right CN activation during reward anticipation and decreased rACC activation during reward outcomes, we calculated an effect size of approximately $z=4.1$. Conservatively, we estimate the effect size for the increased right CN activation and reduced rACC activation will be in the range of $z = (0.75-1.25)$. Our models thus have >90% power at $\alpha=0.025$.

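### Target engagement is written as two regional changes joined by 'and', but no rule covers a one-region result, and >90% power does not hold for both regions at the lower planned effect if that effect is a between-arm difference

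*Combined protocol and SAP*

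**What the plan says.** All references are to the combined protocol and SAP.

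- **Endpoint.** Section 6.1 reads "Increase in right CN activation during reward anticipation and decrease in rACC activation during reward outcomes". Sections 2.1 and 6.4 repeat the same pair, also joined by 'and', and add that the changes must exceed those under MBCT.
- **Test.** Section 6.4 specifies a 2 × 2 × 2 ANCOVA (treatment, region, time) and says "The Treatment × Time interaction beta will be used to evaluate whether BATA produces changes in neural responses to reward anticipation and reward outcomes". By region it says only that post-hoc "comparisons will compare change across each region". It gives no alpha and no statement of what a result in one region would mean.
- **Power.** Section 6.5 expects effects of 0.75 to 1.25, labelled z, and concludes "Our models thus have >90% power" at alpha 0.025. It does not say whether alpha is one- or two-sided, or whether the figure applies to one region, both, or at least one.
- **Numbers.** The synopsis states that "60 subjects will be randomized such that half will receive BATA and half will receive MBCT". Section 4.7 defines dropout and section 6.4 restricts post-treatment assessment to those with at least two therapy sessions, but no dropout rate is given.

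**The concern.** The wording of the endpoint asks for both regions. The named test is a single coefficient, and the single power figure is tied to no rule. If right CN responds and rACC does not, or the reverse, the 'and' implies failure, but no decision rule says so. The post-hoc comparisons would supply material for a claim of engagement, so the verdict could be settled after the data are seen.

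The single coefficient does not fill the gap. The predicted changes have opposite signs, so a Treatment × Time effect averaged over regions tends to cancel when both predictions are true, unless one region is sign-reversed. No such coding is stated.

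The missing rule also decides whether the power claim is right, because power for both regions and power for at least one differ widely at the lower planned effect.

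**Working it through.** **Inputs.** From the documents: 60 randomised, so 30 per arm (synopsis); effects of 0.75, 1.0 (mid-range) and 1.25, and alpha 0.025 (section 6.5). Assumed: the effect d is a standardised between-arm difference in change, equal in the two regions; no loss; independent regions unless stated.

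**Step 1: the plan's own figure, one region.** Two-sample t test, df = 58, noncentrality = d × √(30/2). At d = 0.75 this is 0.75 × 3.873 = 2.905.
- Two-sided 0.025, critical value 2.301: power p = 72.6%.
- One-sided 0.025 (the same power as two-sided 0.05), critical value 2.002: p = 81.5%.

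So >90% is not reproduced at 0.75. It is reached at 1.0 (93.9% and 96.8%).

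**Step 2: rules for two independent regions.** Both = p²; at least one = 1 − (1 − p)²; exactly one = 2p(1 − p).

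| d | Alpha | One region | Both | At least one | Exactly one |
|---|---|---|---|---|---|
| 0.75 | two-sided 0.025 | 72.6% | 52.7% | 92.5% | 39.8% |
| 0.75 | one-sided 0.025 or two-sided 0.05 | 81.5% | 66.4% | 96.6% | 30.2% |
| 1.0 | two-sided 0.025 | 93.9% | 88.2% | 99.6% | 11.5% |
| 1.0 | one-sided 0.025 or two-sided 0.05 | 96.8% | 93.6% | 99.9% | 6.3% |
| 1.25 | two-sided 0.025 | 99.4% | 98.7% | >99.9% | 1.3% |
| 1.25 | one-sided 0.025 or two-sided 0.05 | 99.7% | 99.5% | >99.9% | 0.5% |

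**Step 3: correlated regions, d = 0.75.** At correlation 0.5 (rACC sign-reversed, bivariate normal with the same p), both = 59% or 71%. Exactly one = 2(p − both) = 27% or 21%. At least one = 2p − both = 86% or 92%.

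**Step 4: loss to follow-up, d = 0.75, independent regions.**

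| Analysed per arm | Alpha | One region | Both | Exactly one |
|---|---|---|---|---|
| 27 | two-sided 0.025 | 67.3% | 45.3% | 44.0% |
| 27 | two-sided 0.05 | 77.2% | 59.6% | 35.2% |
| 24 | two-sided 0.025 | 61.2% | 37.5% | 47.5% |
| 24 | two-sided 0.05 | 72.0% | 51.9% | 40.3% |

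**Step 5: a paired within-arm reading.** If 0.75 is a paired effect in the 30 BATA participants, noncentrality = 0.75 × √30 = 4.108 with df = 29 and critical value 2.364 (two-sided 0.025). Power is 95% per region and 0.954² = 91% for both.

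**Step 6: the single coefficient, d = 0.75.** Averaged over regions, the expected effect is (0.75 − 0.75)/2 = 0. With rACC sign-reversed, the standardised effect is 0.75/√((1 + ρ)/2). By normal approximation at two-sided 0.025, power is 97% at ρ = 0 and 87% at ρ = 0.5. That contrast cannot tell 0.75 + 0.75 from 1.5 + 0, so it does not establish both changes.

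**The case against.** The best reply is that the plan has one primary statistic, that 'and' is used consistently, and that a one-region result therefore already means not shown. The consistent wording is a fair point, and it is why the fix below follows it. But the named statistic does not test the conjunction (step 6), and no text attaches a decision to the regional results.

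Four stronger readings are tempting, and the documents do not support them.

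- **The >90% is simply wrong.** This is not shown. Section 6.5 ties its effect to pilot change in activation and never calls it a between-arm difference. A paired reading gives 91% for both regions (step 5), though it would not address the comparison with MBCT. A between-arm either-region rule gives 92.5% if the regions are independent.
- **Alpha 0.025 is 0.05 split over two regions.** It may be, but the endpoint is directional and one-sided 0.025 is equally possible.
- **Family-wise error is inflated.** Claiming on either of two independent regions at 0.05 would give 1 − 0.95² = 9.75%, but the plan never states that rule. At its own 0.025 the figure is 1 − 0.975² = 4.9%.
- **A split result has at most a 2 in 5 chance.** The 40% is not a ceiling: it is 44% to 48% with 10% to 20% loss. It is 27% at correlation 0.5, 30% if alpha is one-sided, and about 1% at d = 1.25.

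**Conclusion.** The point holds as a gap in the success rule, with a power statement that cannot be matched to the endpoint. No section says how a one-region result is judged, and the single coefficient does not test the two changes jointly.

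For a between-arm contrast at 0.75 with 30 analysed per arm, power for both regions is 53% (two-sided 0.025) or 66% (one-sided 0.025) under independence, and 59% or 71% at correlation 0.5. Dropout lowers these. At 1.25 joint power is about 99%, so the shortfall lies at the lower end of the planned range. The sizes rest on reading z as a standardised between-arm difference and on the assumed correlation and retention, none of which section 6.5 gives. The absence of a rule rests on the text alone.

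**What to change.** **Sections 6.1 and 6.4.** Make the region-specific Treatment × Time contrasts for right CN and rACC the primary tests, in place of the pooled coefficient. State that target engagement requires both to be significant in the predicted direction, each at two-sided 0.05, together with change in the predicted direction within BATA. No alpha split is needed, because a claim that requires both tests has error no larger than one test. The within-BATA condition is needed because a between-arm difference could arise from change under MBCT alone, which would not meet section 6.1. Report a one-region result as partial evidence only. Fix the rule before any outcome data are examined by arm.

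**Section 6.5.** State sidedness, what z means, and the assumed dropout and inter-region correlation. Replace >90% by joint power across the range. For the between-arm contrasts at two-sided 0.05 with no dropout, this is about 66% to 71% at 0.75 (correlation 0 to 0.5), 94% at 1.0 and 99% at 1.25. At 0.75 with independent regions it is 60% with 27 per arm and 52% with 24.

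**If the sponsor intends either region to suffice,** it should change the 'and' wording and keep 0.025 per region. That is a legitimate design choice, but it is not the endpoint now written.

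**Cost.** Wording only, with no new data or participants. The stated power becomes less favourable at the low end, and a one-region result can no longer be called success.
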